7.3 Covariates and Subgroups

If applicable, covariates for analyses (e.g. multivariate regression analysis) will be chosen whether they are expected to have an important influence on endpoints of this study according to literature recherche. Selection of these variables for the final model will be performed by a forward stepwise selection process.

Analyses of subgroups in accordance with covariates which may have an important influence on endpoints may be performed. Covariates will be selected by literature recherche.

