4.1 Study Objectives

The aim of the study is to find out to what extent intra-operative positive suggestions delivered to a patient during surgery influence post-operative pain. This will be measured through the Numerical Rating Scale (NRS) and the patient's requirement of pain medication.

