8.2 Demographic and Baseline Variables

The following variables are considered to be demographic and baseline:

- Medical condition (diseases, medication). Type of surgery.
- Age, sex.
- Pre-operative NRS, HGSHS-5, STAI-S, and Apfel score.
- Duration of surgery.
- Intra-operative analgesic drug dose (opioids and non-opioids).
- Intra-operative analgesic co-medication.
- Intra-operative antiemetic medication.

Demographic and baseline values will be grouped by treatment groups. If applicable, subgroups may be used in accordance with section 7.3. Differences between groups will be investigated as follows: Student's t-test for normally distributed continuous variables, Mann-Whitney U test for not-normally distributed continuous variables, and Pearson's chi-squared test for categorical variables. Tests will be performed two-sided. A p-value of less than 0.05 will be considered to be statistically significant. Demographic and baseline values with p-value will be presented as a table.

9 Efficacy Analyses

For statistical analyses of outcome variables, values will be grouped by treatment groups. If applicable, subgroups may be used in accordance with section 7.3. All continuous, normally distributed variables will be summarized using the following descriptive statistics: n (non-missing sample size), mean, standard deviation (SD). All continuous, not-normally distributed variables will be summarized using the following descriptive statistics: n (non-missing sample size), median, interquartile range (IQR). The point estimates and 95% CI (based on the non-missing sample size) of observed levels and absolute difference of percentage points with 95% CU as well will be reported for categorical measures.

Differences between groups will be investigated as follows: Student's t-test for normally distributed continuous variables, Mann-Whitney U test for not-normally distributed continuous variables, and Pearson's chi-squared test for categorical variables. Tests will be performed two-sided. A p-value of less than 0.05 will be considered to be statistically significant.

Effect sizes for outcome variables will be described by Cohen's d with 95% confidence interval. For dichotomous outcome variables, differences between groups will be expressed as number needed to treat (NNT).

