If applicable, all assumptions for regression models will be assessed by viewing plots of the residual values. Analyses of categorical efficacy measures will be performed using logistic regression. Multivariate regression models will be built by a forward stepwise selection process of possible covariates in accordance to literature research.

Results of efficacy analyses will be presented as tables or in text in the final publication(s), including p-values, effect size and NNT.

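### The adjusted efficacy model is left to forward stepwise selection, the deciding analysis is not named, and intra-operative variables labelled as baseline are not barred as covariates

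*SAP*

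**What the plan says.** **Model building.** Section 7.3 provides for covariates where applicable. They "will be chosen whether they are expected to have an important influence on endpoints of this study according to literature recherche", and then "Selection of these variables for the final model will be performed by a forward stepwise selection process". Section 9 says the same of the efficacy models: "Multivariate regression models will be built by a forward stepwise selection process of possible covariates in accordance to literature research". Neither section names a candidate, gives an entry or stopping criterion, or says that treatment stays in the model.

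**Tests.** Section 9 prescribes t, Mann-Whitney and chi-squared tests, two-sided at 0.05. It then adds, without condition, logistic regression for categorical efficacy measures. Section 9.1 sends the primary endpoint to section 9 as a whole.

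**Baseline list.** Section 8.2 opens with "The following variables are considered to be demographic and baseline". The list includes duration of surgery, intra-operative analgesic dose, intra-operative analgesic co-medication and "Intra-operative antiemetic medication". Section 4.1 describes the question as how far "intra-operative positive suggestions delivered to a patient during surgery influence post-operative pain". The table in section 5.4 records these four items at the end of surgery (two of them also at 24 hours) and none of them in its Baseline column.

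**The concern.** Three things are left loose.

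- **The adjusted model is not pre-specified.** The literature narrows the pool, but the outcome data choose the final terms. A pre-operative value of the same scale as the outcome (NRS for pain, STAI-S for anxiety) may drop out.
- **A categorical endpoint has two analyses and no stated priority.** A logistic model with treatment alone would answer almost the same question as the chi-squared test. The two can part once covariates enter, and the choice between them could then be made after seeing both.
- **The baseline label is wrong for variables that arise during the intervention.** If the audio changed how much drug was given, that change would be part of its effect. Conditioning on the dose would remove that part and estimate something other than the total effect that section 4.1 asks about.

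**Working it through.** **1. The plan's own figure.** Inputs from section 6: d = 0.3, two-sided alpha 0.05, 80% power, 1:1, total 368.

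- Normal approximation: 2 × (1.960 + 0.842)² / 0.3² = 174.4, so 175 per arm, 350 in total.
- Noncentral t: 176 per arm, 352 in total.
- Mann-Whitney with normal data: efficiency 3/π = 0.955, so 184 per arm is worth 184 × 0.955 = 175.7. Power is 80.1% at 368 in total, an exact match.

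Section 6 does not name the test, but the figure fits an unadjusted comparison. A t-test with 184 per arm has noncentrality 0.3 × √(184/2) = 2.88 and power 81.9%, the reference value below.

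**2. Does the selected model vary?** Simulation with N = 368, a continuous outcome, 11 candidates, entry at p<0.05 and treatment forced in (settings assumed, since the SAP gives none). Each scenario of 1000 trials produced 45 to 49 different covariate sets from a single design. With 12 candidates and 4000 trials there were 117.

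**3. False positives with no treatment effect, treatment forced in.**

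| Simulation | Unadjusted | Stepwise | Either p<0.05 |
|---|---|---|---|
| 2000 trials, 12 candidates, one with R² = 0.2 | – | 5.5% | 7.2% |
| 4000 trials, same design | 5.3% | 4.8% | 7.1% |
| 1000 trials, 11 candidates | 4.7% | 4.7% | – |

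The 5.5% is compatible with 5%: the Monte Carlo standard error is √(0.05 × 0.95 / 2000) = 0.49 points, p = 0.30. Stepwise selection alone shows no inflation here. The rise to about 7% comes from having two answers to choose from. These runs use a linear model, so they only indicate the size for a chi-squared and logistic pair.

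**4. Treatment not forced in.** The SAP does not exclude this. When treatment competed as a candidate, its mean estimate in the trials that kept it was 0.256 against a direct effect of 0.225, and 0.230 against 0.150 (25% and 50% of the effect through dose). Estimates kept because they were large are too large.

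**5. Adjusting for an intra-operative dose.** Assumptions, none from the SAP: continuous outcome and dose, each with SD 1 within arm; 25% of the 0.3 effect runs through dose; dose-outcome slope c. The adjusted effect is 0.75 × 0.3 = 0.225. Dose also explains outcome variance, so the residual SD is √(1 − c²). The arms differ in dose by δ = 0.075/c, which costs a factor √(1 − r²) with r² = (δ²/4)/(1 + δ²/4). Noncentrality = 0.225 × √(1 − r²) × √92 / √(1 − c²).

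| c | Residual SD | r² | Noncentrality | Power |
|---|---|---|---|---|
| 0.3 | 0.954 | 0.015 | 2.24 | 61% |
| 0.4 | 0.917 | 0.009 | 2.34 | 65% |
| 0.5 | 0.866 | 0.006 | 2.49 | 70% |
| 0.6 | 0.800 | 0.004 | 2.69 | 77% |

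Simulation at c = 0.5, with other prognostic covariates also selectable, shows how far this depends on the assumed share:

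| Share through dose | Adjusted estimate | Adjusted power | Unadjusted power |
|---|---|---|---|
| 0% | 0.297 | 94.7% | 80.3% |
| 25% | 0.225 | 78.3% | 83.0% |
| 50% | 0.148 | 41.4% | 80.8% |

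**6. Gain from fixed covariates.** For a continuous outcome, noncentrality is 0.3 × √92 / √(1 − R²). With R² = 0.1 (assumed) it is 3.03 and power is 85.7%; with R² = 0.2 it is 3.22 and 89.4%.

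**The case against.** - **No passage puts an intra-operative dose into a model.** Section 8.2 governs a descriptive table, and section 7.3 draws covariates from the literature, not from that table. This stands. A reader might infer that the SAP plans to adjust for the doses; it only leaves that open.
- **Treating staff are blinded (section 5.3),** so they cannot dose by allocation. This makes an effect on dose less direct. It does not exclude one, because a patient's response to the audio could still alter dosing. The 25% share has no support in the SAP.
- **Stepwise selection does not inflate the type I error of the treatment test.** With treatment forced in, this stands. A reader might infer inflation from selection alone, but the simulations do not show it. The 7% also needs a rule that either result counts, which the SAP does not state.
- **Power after adjusting for a mediating dose could be put at 58%,** by placing 0.225 in an unadjusted t-test. That ignores the variance the dose explains, so the 61–77% range replaces it.
- **Not every endpoint has two analyses.** The 0.05 threshold is attached to the simple tests, adjustment is conditional, and the unconditional regression sentence covers categorical measures only. This stands, and the point is limited to them. The primary endpoint, requirement of pain medication, may be one.

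**Conclusion.** The point holds for the adjusted analyses. The SAP states a data-driven method for a model it could fix in advance, does not say which analysis decides a categorical endpoint, and labels as baseline four items that its own section 5.4 records after surgery. The unadjusted tests are not affected, so this is a change the sponsor should make rather than a flaw that invalidates the trial.

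The possible cost is a false-positive rate of about 7% if either result were accepted. Separately, any part of the effect that runs through an intra-operative variable would be lost if that variable were adjusted for: 0.30 becomes 0.225 under an assumed 25% share, with power of 61–77% for assumed slopes of 0.3 to 0.6. If no effect runs through dose, there is no such loss.

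**What to change.** - **Sections 7.3 and 9:** delete forward stepwise selection. Pre-specify one adjusted model per endpoint, with treatment forced in and all terms kept: centre, type of surgery, pre-operative NRS and pre-operative STAI-S, plus Apfel score for the PONV and antiemetic endpoints. The exact set is a judgement. HGSHS-5 is also collected and, if wanted, should be named now. The schedule in section 5.1 places the Baseline column after Randomization, so define the covariates as measured before the audio starts and without knowledge of allocation.
- **Section 9.1:** state that the unadjusted section 9 test decides and that the adjusted model is supportive. This agrees with the sample size, which reproduces as an unadjusted calculation.
- **Section 8.2:** move duration of surgery and the intra-operative drugs to a separate intra-operative table, and bar them as covariates in efficacy models.

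The cost is wording only, since these variables are already collected and centre is known. The downside is a few degrees of freedom if a covariate is not prognostic. For a continuous outcome, assumed R² of 0.1–0.2 would raise the power of the adjusted analysis from 82% to 86–89%; this gain does not carry over directly to a binary endpoint.

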7.4 Missing Data

Missing data will be excluded from each specific statistical analysis and reported.

7.5 Interim Analyses and Data Monitoring

Interim analyses are not planned.

7.6 Multi-center Studies

Patients from all 5 participating study centers will be combined for final analysis. This will be performed by the coordinating study center, University Knappschaftskrankenhaus Bochum. Therefore, data of each study center will be transferred to Bochum. Before transfer, data will be pseudonymized. An excel sheet for documentation of study variables will be provided for each study center.

8 Summary of Study Data

All continuous, normally distributed variables will be summarized using the following descriptive statistics: n (non-missing sample size), mean, standard deviation (SD). All continuous, not-normally distributed variables will be summarized using the following descriptive statistics: n (non-missing sample size), median, interquartile range (IQR). The frequency and percentages (based on the non-missing sample size) of observed levels will be reported for all categorical measures of baseline characteristics. Moreover, for dichotomous outcomes point estimates and 95% CI and absolute differences as difference of percentage points and 95% CI will be calculated. In general, all data will be listed, sorted by site, treatment and subject, and when appropriate by visit number within subject. All summary tables will be structured with a column for each treatment in the order (Control, Intervention) and will be annotated with the total population size relevant to that table/treatment, including any missing observations.

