5.3 Randomization and Blinding

Patients are assigned in a 1:1 ratio to intervention or control group by simple randomization technique (drawing lots), for each study center.

This is a double-blinded trial. Assignment to treatment group and conduct of study procedure is performed by independent study personnel, which is not involved in conduct of general anesthesia or post-operative treatment of pain. Medical personnel which is involved in treatment of the patient has no information about group allocation. Headphones of the audio player for therapeutically communication are placed on the ears of patients in control group as well (whereas no audio file will be played).

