On basis of a 1:1 randomization ratio, we calculated that a planned sample of 368 patients would provide the trial with approximately 80% power to detect a difference in postoperative pain therapy on the basis of an effect size of 0.3 at a two-sided alpha level of 0.05. With 5 participating study centers, approximately 70-80 patients need to be included per center.

The sample size calculation is based on a previously published meta-analysis by Rosendahl et al.⁷ Sample size calculation for a power of 80% was done using G*Power software (University Dusseldorf, Dusseldorf, Germany, http://www.psychologie.hhu.de/arbeitsgruppen/allgemeine-psychologie-undarbeitspsychologie/gpower.html).

⁶ Apfel CC, Korttila K, Abdalla M, et al. A Factorial Trial of Six Interventions for the Prevention of Postoperative Nausea and Vomiting. N Engl J Med 2004; 350(24): 2441-51.

⁷ Rosendahl J, Koranyi S, Jacob D, Zech N, Hansen E. Efficacy of therapeutic suggestions under general anesthesia: A systematic review and meta-analysis of randomized controlled trials. BMC Anesthesiol 2016;16(1).

 Caseley-Rondi et al. 1994; d = 0.459
 Korunka et al. 1992; d = 0.405
 Rosenberg et al. 1992; d = 0.384
 Williams et al. 1994; d = 0.323
 Mastropietro et al. 1998; d = 0.315
 Furlong-Read et al. 1993, d = 0.256
 Nilsson et al. 1993; d = 0.244

7 General Considerations

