9.1 Primary Efficacy Analysis

Analysis of primary endpoint (post-operative pain medication at 2- and 24-hours post-surgery) will be performed in accordance with section 9.

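### Lots are drawn centre by centre, but the planned tests ignore centre: under the stated simple randomisation they stay valid but lose some precision

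*SAP*

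**What the plan says.** - **Allocation (SAP Section 5.3).** Patients are allocated 1:1 "by simple randomization technique (drawing lots), for each study center". Each centre therefore has its own randomisation. The section does not say whether a centre's lots come from a set with equal numbers for each arm or are independent draws.
- **Size (Section 6).** "With 5 participating study centers, approximately 70-80 patients need to be included per center". The planned total is 368, for about 80% power at an effect size of 0.3 and a two-sided alpha of 0.05. No centre term is mentioned.
- **Centres in the analysis (Section 7.6).** "Patients from all 5 participating study centers will be combined for final analysis". The rest of that section covers data transfer and documentation. Elsewhere, Section 8 uses site to sort the data listings.
- **Tests (Section 9).** "Student's t-test for normally distributed continuous variables, Mann-Whitney U test for not-normally distributed continuous variables, and Pearson's chi-squared test for categorical variables", all without strata. Under Section 9.1 the primary analysis "will be performed in accordance with section 9", so it uses these same tests.
- **Covariates (Sections 7.3 and 9).** Adjustment is optional, with candidates taken from the literature. "Selection of these variables for the final model will be performed by a forward stepwise selection process". Centre is not named.

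**The concern.** An analysis should normally reflect the groups within which patients were randomised. Here the randomisation was run by centre and the tests take no account of it. The primary endpoint is post-operative pain medication. Section 5.4 lists several opioids and non-opioids, and Section 5.2 admits both neurosurgery and abdominal-gynaecological surgery, so hospitals could plausibly differ in how much analgesia they give. Any such difference is left as noise around the treatment comparison. The optional stepwise models are no safeguard, because they may not be fitted and need not retain centre if they are.

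What is at stake is precision, in a trial planned at only about 80% power. The risk of a false positive finding is not raised.

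**Working it through.** **Inputs.** From Section 6: 368 patients, 1:1 (184 per arm), effect size 0.3 read as Cohen's d, two-sided alpha 0.05, five centres. Assumed, because the SAP gives no figure: the share ρ of outcome variance explained by centre, taken as 2%, 5%, 10% and 20%. The outcome is treated as continuous and roughly normal.

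**Step 1: reproduce the 368.** A two-sample t-test needs 352 patients. A Mann-Whitney calculation with asymptotic relative efficiency 3/π reproduces the SAP:
- effective n per arm = 184 × 3/π = 175.7
- noncentrality = 0.3 × √(175.7/2) = 2.812
- degrees of freedom = 2 × 175.7 − 2 = 349.4, critical t = 1.967
- power = 80.1%, and 184 per arm is the smallest size that reaches 80%.

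**Step 2: put centre in the analysis.** Adjustment removes the share ρ, so the residual SD becomes √(1−ρ) and the noncentrality becomes 2.812/√(1−ρ). The equivalent size of a trial analysed without centre is 368/(1−ρ).

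| ρ (assumed) | Noncentrality | Power | Equivalent N | Unadjusted SE / adjusted SE |
|---|---|---|---|---|
| 0 | 2.812 | 80.1% | 368 | 1.00 |
| 2% | 2.840 | 80.9% | 376 | 1.01 |
| 5% | 2.885 | 82.0% | 387 | 1.03 |
| 10% | 2.964 | 84.0% | 409 | 1.05 |
| 20% | 3.144 | 88.0% | 460 | 1.12 |

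**Step 3: check by simulation.** Five centres of 74 patients, 20,000 runs per setting, fixed centre effects, t-test against a linear model with centre. For power, d = 0.3.

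| Lots | ρ | Power, pooled | Power, with centre | Type I error, pooled |
|---|---|---|---|---|
| Simple | 5% | 81.5% | 83.1% | 5.2% |
| Simple | 10% | 81.6% | 85.0% | 5.2% |
| Simple | 20% | 81.6% | 88.6% | 4.9% |
| Balanced within centre | 5% | 82.7% | 84.0% | 4.4% |
| Balanced within centre | 10% | 83.2% | 85.7% | 4.0% |
| Balanced within centre | 20% | 84.4% | 89.2% | 2.9% |

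With simple randomisation the pooled standard error matches the true sampling SD (ratio 0.99 to 1.00). With balanced lots it exceeds it by about 2%, 6% and 11-12%.

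The conservative type I error depends a little on how the centre effects are set. A normal approximation, 2Φ(−1.96/√(1−ρ)), gives 3.9% at ρ = 10% and 2.8% at ρ = 20%. Simulations give about 4.0% to 4.1% and 2.9% to 3.3%; drawing the centre effects at random in each run gives values at the upper end.

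A separate simulation of the same layout (8,000 runs) found smaller power gains. At ρ = 2%, 5%, 10% and 20% they were 0.3, 1.2, 2.9 and 6.1 points with simple randomisation, and 0.4, 1.0, 2.2 and 3.7 with balanced lots.

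**The case against.** The strongest reply is that the planned test is not wrong. Section 5.3 states simple randomisation, and under it the pooled comparison has the correct error rate. **This stands**, and it rules out two stronger readings.

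- *A reader might infer that the standard errors, or the error bars, are too wide.* In the strict sense this needs lots balanced within each centre, which the SAP does not state. In Section 11 the error bars are SDs or IQRs, which a centre-adjusted test would not change. The relevant quantity is the standard error of the treatment difference.
- *A reader might infer that chance imbalance within a centre confounds centre practice with treatment.* With independent draws, a 48:32 split or worse has a 9.3% chance in a given centre of 80. That is random variation, which the pooled standard error already includes. It is not bias.

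The size of the gain is also open to challenge. No between-centre variance is given, and at 2% to 5% the gain is only one or two power points. Section 5.4 converts opioids to morphine equivalents and non-opioids to a percentage of the maximum daily dose, which dampens differences in drug choice. Section 4.2 ties the medication requirement to a single NRS threshold. Nothing says that the mix of surgery differs by centre. If the primary endpoint is read as yes/no, the figures above do not carry over directly. These points limit the expected benefit but do not give a reason to leave centre out.

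Finally, the change is not wholly free. A van Elteren test gives a p-value but no Cohen's d, and a logistic model with centre gives a conditional odds ratio, whereas NNT and percentage-point differences are marginal. This stands as a matter of wording that the fix must cover.

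**Conclusion.** The point holds as a modest recommendation on precision. Randomisation is by centre, the analysis ignores centre, and nothing in the SAP guarantees that centre enters any model. Under the stated simple randomisation the primary test is valid. If the lots were in fact balanced within centre, it errs on the conservative side. In neither case is the false positive rate inflated.

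Under the formula, the power given up runs from about 1 point (centre share 2%) to about 8 points (20%), and simulated gains are somewhat smaller with balanced lots. The direction is certain if centres differ. The size rests on the assumed centre share and on a continuous outcome, neither of which the SAP settles. The change is worth making because stratifying by centre is sound under either reading of the lots and removes a choice now left to stepwise selection.

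**What to change.** In Sections 7.6 and 9, prespecify centre in the primary analysis and keep it in every model whatever the stepwise procedure selects:

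- **Doses and NRS:** van Elteren test (Mann-Whitney stratified by centre). Continue to report Cohen's d with its confidence interval, taken from the centre-adjusted mean difference.
- **Yes/no outcomes:** Cochran-Mantel-Haenszel test and a centre-stratified risk difference with its confidence interval, with NNT derived from that difference.
- **Regressions:** centre as a fixed effect.
- **Sensitivity:** keep the pooled tests now in Section 9.

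It would also help to state in Section 5.3 whether the lots were drawn from a balanced set in each centre, since this decides whether the pooled sensitivity test is exact or conservative.

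The cost is SAP wording, four degrees of freedom for five centres, and care in aligning the reported effect measures. Site is already used to sort the listings, and R and SPSS are already named in Section 13.
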